8.2 SAFETY PARAMETERS

- Incidence of persistent sight-threatening complications and adverse events and cumulative events defined per ISO 11979-7.

The incidence of all other adverse events will also be presented.

8.2.2 ADDITIONAL SAFETY ANALYSES

The safety outcomes will be summarized descriptively for all eyes that have the procedure attempted.

BCDVA

Monocular BCDVA will be presented with the number and percent of eyes who fall into each category of BCDVA at each visit (e.g. 20/20 or better, 20/25 or better, 20/32 or better, etc.). The mean BCVDA logMAR score will be calculated for each visit. Change in BCVDA from Postop Week 3 or from Preoperative will be presented at each visit as categorical outcomes of “Increase in 15 letters or more”, “Increase in 10-14 letters”, “Increase in 5-9 letters”, “No change”, “Decrease in 5-9 letters”, “Decrease in 10-14 letters”, and “Decrease in 15 letters or more”.

In-Office Erythropisa Assessment

The number and percent of eyes in each outcome of erythropsia assessment (0- white, 1- pink, or 2- red) will be presented.

Intraocular Pressure (IOP)

The IOP and change in IOP from preoperative will be summarized by mean, standard deviation, median, minimum and maximum. The number and percent of eyes reported with $IOP \geq 25 \text{ mmHg}$ or an IOP increase of $\geq 10 \text{ mmHg}$ from preop will be provided at each visit.

Slit Lamp Examination and Fundus Examination Findings

The outcomes will be summarized descriptively by count and percent of eyes with each possible finding category.

⁸ McAlinden C, Pesudovs K, Moore JE. The Development of an Instrument to Measure Quality of Vision: The Quality of Vision (QoV) Questionnaire. *Invest Ophthalmol Vis Sci*. 2010;51:5537-5545.

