7.3.2 LIGHT TREATMENT PROCEDURE

At the discretion of the Principal Investigator, a subgroup of eyes will receive an [REDACTED] 7-14 days postop. Commencing 17 to 30 days postop, all eyes will receive up to three adjustments and one to two lock-in treatments. Each light treatment will be separated by 2 to 7 days. The type of adjustment (spherocylindrical and/or presbyopia) the study eye receives is dependent on specific criteria at each light adjustment visit.

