7.3.2.1 Postponement of Light Treatment Procedure(s)

LDL treatment should be delayed if any of the following new symptoms or changes in performance are noted;

- Color Vision Testing: Treatment should be delayed if the subject scores worse on Part 2 for Tritan evaluation when compared to the initial pre-light treatment test.
- Erythropsia Evaluation: With any score of 2 (red), the treatment should be delayed.
- Best Corrected Distance Visual Acuity: With any loss of BCDVA (unless the cause is known to be non-retinal) of 10 letters or more on an ETDRS (logMAR) chart when compared to the initial pre-light treatment BCDVA, treatment should be delayed.

The subject should return for follow-up visits until the subject's visual assessment of erythropsia is a score of 0 or 1 (indicates the paper looks white or pink), the BCDVA is within 10 letters of the initial pre-light treatment BCDVA and an equivalent or better score than the initial pre-light treatment test is measured in the Tritan section of the City University Color Test, at which time the next LDL treatment may be delivered.

- If sutures were utilized at the time of surgery to close the incision wound, light treatments should not commence on the study eye until a minimum time after suture removal that has been agreed upon by the Sponsor and the Principal Investigator.
- A study eye with an ocular adverse event that could be negatively impacted by light treatment or negatively impact the effectiveness or safety of a light treatment should have light treatments delayed until after the adverse event has subsided. This includes corneal edema and superficial punctate keratitis (SPK) (Grade 3 (moderate) or more severe), retinal conditions including diabetic retinopathy and cystoid macular edema, epithelial defect, endophthalmitis or any other safety concern that the investigator believes may be negatively impacted by light treatment.
- If a study eye is discovered with evidence of premature photopolymerization as evidenced as a zone on the lens surface, the investigator should contact the Sponsor for further instructions. (see Appendix 1 for additional details regarding premature photopolymerization).
- Any study eye possessing clinically significant posterior capsular (PC) haze should undergo a YAG capsulotomy procedure prior to the adjustment. A minimum of 48 hours

should separate the YAG treatment from the corresponding refraction and LDD adjustment.

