7.3.2.4 Adjustment Procedure(s)

Refer to the LDD Operator's manual for instructions on LDD start up and instructions for the daily alignment test to be performed prior to the first treatment of the day to ensure the UV beam is aligned to the reticle. If the UV beam is not aligned to the reticle within the specifications detailed in the LDD Operator's manual, do not perform treatments and call RxSight customer service immediately.

1. Within the Patient ID and Patient Data screens, follow the touchscreen prompts to enter requested information. Press the "Proceed" button once information has been entered respectively for each screen.
2. Within the Confirmation screen, review all information and press the "Confirm" button.
3. Verify that the LDD ring lights and reticle target are activated.
4. Apply topical anesthetic.
5. Position the RxSight supplied contact lens ($M = 0.766x$, black contact lens) on the cornea using a Sponsor approved coupling medium.

Note: The RxSight contact lens is similar to those used in other ophthalmic procedures in which customized magnification is required. To ensure correct magnification for treatment, use only the RxSight designated contact lens.

6. Instruct the subject to focus straight ahead on the LDD fixation light with the study eye.
7. Using the microscope, focus on the cornea and verify that there are no trapped bubbles present. Confirm alignment of the contact lens by approximately aligning the Purkinje images to the inner circle of the reticle target.
8. For dilated pupil light treatments, using the microscope, focus on the LAL haptics and align the reticle target with the periphery of the LAL. Press the "Ready" button. Initiate the UV exposure as prompted by the LDD display using the trigger. Use the joystick to keep the LAL centered in the alignment reticle. Perform micro adjustments to keep the reticle target centered to the LAL and to keep the LAL in focus. In the case of subject movement, loss of alignment, or loss of focus, pause the treatment, quickly refocus, realign the lens with respect to the reticle beam, and immediately resume treatment to limit the duration of any pauses once the light treatment has been initiated.

Note: Always maintain the LAL in focus by focusing at the haptics. Never focus onto the CCC (capsulotomy) or Purkinje images.

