The LAL must be implanted following specific surgical procedures. If these procedures are not followed by the surgeon, the lens may become scratched or improperly placed in the eye and may need to be explanted prior to light treatments. In order to perform the lens adjustment or the lens lock-in procedures, the subject's pupil needs to be adequately dilated. If this cannot be accomplished for any reason, additional eye drops, injections into the eye, or surgery may need to be utilized to adequately dilate the pupil. If the pupil cannot be adequately dilated after these types of treatments, the LAL may need to be explanted. An unpredicted change in vision can occur resulting from ocular exposure to daylight or any other UV source before the LAL is locked-in. The light treatments may not improve vision and/or manifest refraction, and the adjustment/lock-in procedure may make vision worse, such that it may be necessary to remove and replace the LAL. Vision loss may be permanent and may not be improved by replacing the LAL. There is a potential risk for UV-induced damage to the eye, including the cornea and retina, which may be permanent. UV light can sometimes cause a reactivation of previous herpes virus infection in the eye. A reactivation of herpes virus can cause scarring of the cornea, blurred vision, eye pain, extreme light sensitivity, permanent loss of vision, and possible need for corneal transplant. Temporary or persistent erythropsia and/or temporary or persistent color vision deficiency may occur. Corneal dryness and corneal abrasions from the lens used for adjustment and lock-in can occur. After the lens adjustment(s) or after the lens lock-in procedures, discomfort, itching and light sensitivity may occur. In cases where a spherocylinder adjustment is performed, it

is possible that visual disturbances may occur if the IOL rotates or if the correction is not performed on the correct axis of astigmatism.

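### Slit-lamp and fundus findings are tabulated with no within-eye reference exam, so for low-grade transient corneal signs the planned table gives only a range for new onset

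*Combined protocol and SAP*

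**What the plan says.** For slit-lamp and fundus results, the whole plan in Section 8.2.2 is: "The outcomes will be summarized descriptively by count and percent of eyes with each possible finding category". The sentence gives no reference exam and no rule for a new or worsened finding. Unlike the acuity text, it does not say that results are shown by visit.

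The same section treats baseline in three ways:

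- Best corrected acuity has a within-eye reference: "Change in BCVDA from Postop Week 3 or from Preoperative will be presented at each visit as categorical outcomes of" letters gained or lost.
- Intraocular pressure has one too, but only preoperative: "The IOP and change in IOP from preoperative will be summarized by mean, standard deviation, median, minimum and maximum".
- Erythropsia has none: "The number and percent of eyes in each outcome of erythropsia assessment" is presented. Section 10.1 does make a score of 2 after the first light treatment a reportable adverse event.

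On exposure, Section 7.3.2 says that from days 17 to 30 "all eyes will receive up to three adjustments and one to two lock-in treatments". Sections 7.3.2.4 and 7.3.2.5 place a contact lens on the cornea at each of these ("Position the RxSight supplied contact lens"). Section 10.6 warns: "Corneal dryness and corneal abrasions from the lens used for adjustment and lock-in can occur".

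On the corneal state at first treatment, Section 7.3.2.1 delays treatment for ocular adverse events that light could worsen: "This includes corneal edema and superficial punctate keratitis (SPK) (Grade 3 (moderate) or more severe".

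Table 1 schedules the slit lamp at Week 3 and every scheduled visit after it. After Week 3, the fundus exam is scheduled only at Months 3 and 6.

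**The concern.** Every eye has cataract surgery and then, a few weeks later, a series of UV treatments through a contact lens. The useful safety question for exam findings is which of them appeared after light treatment began. Surgical signs may be fading over the same weeks in which treatment-related signs appear. A table of affected eyes per category mixes the two: a flat or falling count can hide new onset, because eyes that clear offset eyes that become affected.

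At stake is a descriptive safety count. No endpoint, sample size or test depends on it.

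**Working it through.** The documents state no expected finding rate and no sample size calculation, so there is no planned figure to reproduce. The check asks what the planned table can and cannot reveal.

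**Inputs from the documents**

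- Eyes: at most 200 in up to 100 subjects (Section 6).
- Light treatments per eye: up to 3 adjustments + 2 lock-ins = 5, each with a lens on the cornea (Sections 7.3.2, 7.3.2.4, 7.3.2.5).
- Slit-lamp exams after Week 3: Adjustment #2, Adjustment #3, Lock-in #1, Lock-in #2, Post Lock-in, Month 3 and Month 6 = 7. Three of these visits (Adjustments #2 and #3, Lock-in #2) happen only if needed (Table 1).
- Fundus exams after Week 3: 2 (Table 1).

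**Formula**

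Read the planned table as by visit, which is the favourable reading. Among n eyes examined at both visits, let a have the finding before light treatment and b have it later. The number with it at both visits lies between max(0, a + b − n) and min(a, b). New onset is b minus that number, so it lies between max(0, b − a) and min(b, n − a).

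**Results with n = 200; a and b are assumed**

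| a (before) | b (later) | Low end | High end |
|---|---|---|---|
| 20 | 20 | 0 | min(20, 180) = 20 |
| 40 | 20 | 0 | min(20, 160) = 20 |
| 20 | 25 | 5 | min(25, 180) = 25 |
| 2 | 10 | 8 | min(10, 198) = 10 |
| 0 | 10 | 10 | min(10, 200) = 10 |

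With n = 100 the ranges are the same. In the first row, 20 new among 200 − 20 = 180 eyes at risk would be 11.1%.

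**What drives the width**

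If a fraction r of the earlier findings resolves, new onset = b − a + r·a. For a = 20 and b = 25:

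- r = 0 gives 5.
- r = 0.5 gives 5 + 10 = 15.
- r = 1 gives 5 + 20 = 25.

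So the ambiguity needs a finding that is already present in a fair number of eyes before treatment and that then resolves. With r = 0 or a = 0 the planned table gives the answer exactly.

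**Which findings meet that condition**

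- Low-grade punctate keratitis or dryness: plausibly yes. The stated delay threshold lets milder keratitis be present at Adjustment #1. Dryness from the lens is a named risk, and so is UV damage to the cornea (Section 10.6).
- Lens abrasions: hardly. They cannot predate an eye's first lens placement, and Section 7.3.2.1 lists epithelial defects, with no grade attached, as a reason to delay. So a should be near zero.
- Persistent findings: no, because r = 0.
- Fundus findings: little gain. A finding that appears and clears between Week 3 and Month 3 is never examined, and no table can recover it.

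**The case against.** The strongest reply is that adverse event reporting already does this job. Section 10.1 counts untoward clinical signs as adverse events whether or not the device caused them. Section 10.4.1 requires ocular events to be documented, including those arising from a test result, and treats worsening of a pre-existing condition as an event. Section 8.2 presents their incidence. This largely stands. What it leaves open is the low-grade sign: filing rests with the investigator, and no visible rule says when a mild corneal sign becomes an event.

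A reader might infer that new findings cannot be counted at all. The documents do not support that. The exam data are collected per eye and visit, Section 5 allows additional analyses, and the table could be built later. What is missing is a planned table, not information.

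A reader might also infer that permanent damage or lens abrasions would be hidden. The formula shows otherwise: where nothing resolves, or nothing was present before, the planned counts suffice.

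Two further inferences go beyond the text. One is that corneal edema delays treatment only from Grade 3; the grade may attach to punctate keratitis alone, and the list is illustrative. The argument for keratitis holds either way. The other is that the planned categories hide worsening within a category; the visible text does not define the categories, and they may already be grades.

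Finally, counts per category are an ordinary summary for an exploratory study with no hypothesis-driven endpoints (Sections 3 and 9.1). That is fair, and it limits the weight of the point.

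**Conclusion.** The point holds in a narrow form. Section 8.2.2 gives slit-lamp and fundus findings no within-eye reference to the last exam before light treatment. For low-grade transient corneal signs that may already be present at Week 3, the planned table alone yields a range for new onset: 0 to 20 eyes when 20 are affected at both visits, narrowing to 8 to 10 for 2 then 10. The practical gap is such signs that are not filed as adverse events.

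This is a minor, worthwhile improvement. It rests on three assumptions:

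- The counts are illustrative. If few eyes have the sign at Week 3, the gap nearly closes.
- Surgery can leave such signs at Week 3 and light treatment can bring them back. The delay rule and Section 10.6 make this plausible but give no rates.
- The Week 3 exam is done before Adjustment #1 at the same visit.

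**What to change.** Keep the planned table, state that it is by visit, and add this to Section 8.2.2: at each post-treatment visit, the number and percentage of eyes with a new or worsened (by recorded grade where the finding is graded), unchanged or resolved finding, relative to the last exam before that eye's first light treatment. The denominator is the eyes examined at both visits.

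Define the reference exam now:

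- Normally, the Week 3 exam before Adjustment #1. This includes former CSP-037-MX eyes, which have no preoperative visit in this study.
- If the redacted Day 7 to 14 step is a light treatment, that subgroup needs an earlier reference: the slit lamp done at that visit before the treatment, and the preoperative fundus exam, since Table 1 schedules no fundus exam in between.

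Show every visit. A sign that has cleared by Month 6 would not appear in a comparison of Week 3 with Month 6 alone. Label the table as timing relative to light treatment and not attribution, because late surgical events such as cystoid macular edema would also count as new.

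The cost is a few sentences, a few extra safety tables and consistent coding of findings and grades across visits. No visit or test is added. Writing it now fixes the reference exam and the categories before the data are seen, and gives a cross-check on adverse event filing.

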9 SEQUENCE OF PLANNED ANALYSES

9.1 INTERIM ANALYSES

An interim analysis may be performed. Since there are no statistically based hypothesis driven endpoints or associated sample size, no multiplicity adjustment is needed.

9.2 FINAL REPORT

When all enrolled study eyes have completed the Postop Month 6 or later visit or have been discontinued from the study, the data will be analyzed for a final study report.

10 ADVERSE EVENTS

Throughout the study, adverse events are to be documented and reported on Adverse Event Forms (AE Forms) that are included in the study documentation. If an adverse event (AE) occurs, the first concern will be the safety and welfare of the subject; treatment should be provided as appropriate for the event. During the study, the Investigator should appropriately treat and follow each AE until it resolves, stabilizes, or it is determined that further improvement is not expected. Per Section 7.7.1, subjects with ocular serious adverse events or adverse device effects that are unresolved at study exit (Postop Month 6 or later) should continue to be followed until resolution of the event or until they are stable per the investigator's evaluation.

10.1 ADVERSE EVENT (AE) DEFINITIONS

An adverse event is any untoward medical occurrence, unintended disease or injury, or untoward clinical signs (including abnormal laboratory findings) in subjects, users, or other persons, whether or not related to the investigational medical device.

Note 1 to entry: This definition includes events related to the investigational medical device or the comparator.

Note 2 to entry: This definition includes events related to the procedures involved.

Note 3 to entry: For users or other persons, this definition is restricted to events related to investigational medical devices.

The specific event should be reported as an AE:

- An erythropsia score of 2 (red) at any time after the initial light treatment.

10.2 ADVERSE DEVICE EFFECT (ADE) DEFINITION

Adverse event related to the use of an investigational medical device.

Note 1: This definition includes adverse events resulting from insufficient or inadequate instructions for use, deployment, implantation, installation, or operation, or any malfunction of the investigational medical device.

Note 2: This definition includes any event resulting from use error or from intentional misuse of the investigational medical device.

10.3 DEVICE DEFICIENCY (DD) DEFINITION

Inadequacy of a medical device with respect to its identity, quality, durability, reliability, safety or performance. Note: Device deficiencies include malfunctions, use errors, and inadequate labeling.

10.4 SERIOUS ADVERSE EVENT (SAE) DEFINITION

Serious Adverse Events are AEs that lead to:

- death
- a serious deterioration in the health of the subject that:
 - results in a life-threatening illness or injury
 - results in a permanent impairment of a body structure or function (e.g., blindness)
 - requires in-subject hospitalization or prolongation of existing hospitalization
 - results in medical or surgical intervention to prevent permanent impairment to a body structure or a body function
- fetal distress, fetal death, or a congenital abnormality or birth defect
- a potentially sight-threatening condition
- or is another important medical event.

10.4.1 IDENTIFICATION AND COLLECTION

All AEs that occur during the study must be recorded in English on the adverse event Case Report Form. Each event must be on a separate form, regardless of whether one event may be secondary to another or from a single cause. Identification and collection of an AE begins after informed consent has been obtained and documented. Standard sources of identifying AEs include:

- direct observation by the Investigator or study team member
- asking the study participant a specific question (e.g., "Since your last visit, have you experienced any problems with your eyes or vision?")
- unsolicited volunteering of information by the study participant (e.g., "Doctor, I have had numerous headaches since I started using this lens.")

Ocular AEs and SAEs and systemic SAEs observed or elicited by the Investigator, reported by the subject, or resulting from a test result, etc., occurring during the clinical investigation must be documented. AE Forms are to be completed at the time of the event regardless of all data being available.

During the study, the Investigator should treat the study subject as appropriate to ensure his/her safety and welfare. Refer to Section 7.7.1 for additional information pertaining to ongoing AEs at subject exit.

Pre-existing conditions will not be considered AE/SAEs but will be collected at the Preoperative Visit as medical history. A worsening of a pre-existing condition during the study should be documented as an AE and evaluated accordingly.

Hospitalization is a criterion for assessment of seriousness. Hospitalization in the absence of a medical AE is not in itself an AE. For example, the following reports of hospitalization without a medical AE should not be considered either an SAE or an AE:

- Planned hospitalization for a pre-existing condition without serious deterioration in health (e.g., planned knee replacement surgery)
- Social admission (e.g., subject has no place to sleep)
- Administrative admission (e.g., for yearly physical exam or elective procedures not related to the study)
- Optional admission not associated with a precipitation medical AE (e.g., for elective cosmetic surgery)

10.4.2 EVALUATIONS

When evaluating AEs, the Investigator must determine if the event is serious, assess the severity of symptoms, the relationship of the event to the device or study protocol, using the following guidelines:

1. Severity

Mild: subject awareness of a sign or symptom that is easily tolerated, requires no treatment, and does not interfere with subject's daily activities

Moderate: subject awareness of a sign or symptom which may be a low level of concern to the subject and may interfere with daily activities, but can be relieved by simple therapeutic care

Severe: a sign or symptom that interrupts the subject's daily activity and requires systemic therapy or other treatment

2. Relationship (Causality) to Study Device or Study Protocol

Related: There is at least a reasonable possibility that the AE/SAE is related to the study device or study protocol. Reasonable possibility means that there is evidence to suggest a causal relationship between the study device or study protocol and the AE.

Unrelated: There is little or no reasonable possibility that the AE/SAE is related to the study device or study protocol. This assessment implies that the AE/SAE has little or no temporal relationship to the study device and/or a more likely or certain alternative etiology exists.

10.4.3 SAE/UNANTICIPATED ADVERSE DEVICE EFFECT (UADE)/UNANTICIPATED SERIOUS ADVERSE DEVICE EFFECT (SADE) REPORTING

The site should report any event to the Sponsor and its representative in an expedited manner if it meets the criteria for an SAE and/or is an IOL explant from a study eye. Expedited reporting is calling or e-mailing the Sponsor and its representative within 48 hours of becoming aware of the event. Contact details are as follows:

Email: [contact]

Tele: [contact]

When reporting an SAE to the Sponsor and/or its representative, the site should forward any supporting documents along with the SAE Report Form to the Sponsor and its designee within 5 days of the initial communication. Sites must also report the SAE to the reviewing Ethics Committee per its reporting procedures.

An investigator shall submit to the Sponsor and to the reviewing IRB/EC a report of any Unanticipated Adverse Device Effect (UADE) occurring during an investigation as soon as possible, but in no event later than 10 working days after the investigator first learns of the effect or in accordance with National Regulations. As soon as notification of a potential UADE is received by the Sponsor, an investigation will be initiated to determine if the event is a UADE. If the event is confirmed to be a UADE, the regulatory authorities, all other participating Investigators and each reviewing IRB/EC must be notified within 10 working days of the initial report from the site, as applicable or in accordance with National Regulations. If it is determined that the UADE represents an unreasonable risk to study subjects, the study must be terminated within 5 working days following the decision, and no later than 15 working days after first learning of the UADE or in accordance with National Regulations.

